**Patient Population.** We plan to complete 1-year follow-up in 500 patients from a large US-metropolitan area (LA-County) (n=250) and four national metropolitan VA centers (n=250). To account for a dropout rate of ~17%, we will recruit a total of 600 patients. LA-County is one of the largest metropolitan areas in the US. As per October 30, 2020, there were 290,278 laboratory confirmed cases, 24,670 hospitalized patients and 6,999 deaths(104). Since the first reported case of COVID-19 in the US, the four VA sites in Atlanta, Bronx, Houston and Los Angeles, have admitted 847 Veterans. While these sites vary in their COVID-19 experiences, combined they appear to be representative of the National VA population (**Table 1, re-submission Introduction**). These four sites belong to the SUPERNOVA consortium, which is a CDC-funded study ongoing for over 5 years that performs active surveillance for acute gastroenteritis and respiratory infection, including COVID-19 (28). The local site investigators are infectious disease physicians and have study staff trained in enrolling and following patients with infections. Study staff are well versed in identifying patients admitted with COVID-19, using a combination of admission log screening and TheraDoc (clinical surveillance software that integrates with the electronic medical record). Coordinators at the sites are experienced with abstraction of clinical data into REDCap and obtaining, processing, storing and shipping biological specimens. **Inclusion criteria.** Adult COVID-19 patients admitted to the hospital with any symptoms, including pneumonia, ARDS, sepsis, and septic shock(44) will be approached for consent (UCLA Informed Consent Form 20-000763, PI [name]). Since a majority of COVID-19-related deaths and hospitalizations are in male patients, we expect to enroll more men than women (9). **Exclusion criteria.** 1) Lack of consent by either patient or legally authorized representative, 2) <18 years old, 3) COVID-19 re-infection.

**Endpoint Definition.** Clinical composite endpoints will include new onset or worsening frailty, single organ dysfunction, multi-organ dysfunction, and death within one year (primary endpoint) and at time of discharge (secondary endpoint).

**Figure 1.** COVID-19 clinical decision making, study population and primary endpoint [modified after(96)].

**Figure 2.** Study design.

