Hematologic/immunologic White blood cell count Total lymphocyte count Absolute neutrophil count Hematocrit Platelets SARS-CoV-2 antibody	Renal Blood urea nitrogen Creatinine
Inflammatory C-reactive protein Erythrocyte sedimentation rate Procalcitonin Interleukin 6 Ferritin	Hepatic Bilirubin Aspartate transaminase Alanine aminotransferase Lactate dehydrogenase
Cardiac Troponin Creatine kinase MB Brain natriuretic peptide	Coagulation Prothrombin time Partial thromboplastin time International normalized ratio D-dimer
	Chemistries Sodium Glucose Lactate

**Table 1.** Routine laboratory values to be abstracted from electronic medical record.

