**Data Collection.** The data collection method is simple, cost-effective, and minimally invasive, requiring *only one research blood draw at enrollment*, abstraction of clinical parameters from the electronic medical record, and a brief interview at enrollment, at discharge, and at one year. **Clinical Data.** Demographics, laboratory values, organ function parameters, frailty parameters, comorbidities, disability data as well as COVID-19 treatment data will be collected. **Table 1** summarizes the *routine clinical laboratory values* to be collected. Validated *organ function scores*, such as SOFA score, MELD-XI score, the Seattle Heart Failure Model will be calculated(105-107). *Comorbidities* will be assessed using Charlson and Elixhauser scoring systems(108, 109). Risk of alcohol use disorders will be assessed with AUDIT-C (110). *National Health Service Frailty Scale* scores will be assessed(111). All clinical data will be collected at baseline, at discharge and at one year after COVID-19 enrollment, abstracted into REDCap, and later analyzed using R (Vienna, AU). All patients will be interviewed in person (if not available, then by televisit) at discharge and one year after enrollment. *The National Death Index* will be searched for subjects who are uncontactable(112). **Blood Collection and Processing.** Research blood will be collected within 72h of admission and COVID-19 diagnosis confirmation and processed within 2h of sampling, into one 8 ml CPT tube (BD Biosciences) for PBMC transcriptomic analysis and cfDNA analysis and one 8 ml ACD tube (BD Biosciences) for immunophenotyping and cytokine concentration analysis. Each study site will isolate plasma and PBMC using standard procedures, aliquot these samples in duplicates and store samples at -80°C. Samples will be shipped in batches to UCLA on dry ice by express delivery. **cfDNA Sequencing.** The Illumina NovaSeq platform will be used to sequence paired-end reads of cfDNA for 2x150 bp with 1% Phix control using S4 flow cell. For cfDNA concentration quantification, we will use Invitrogen Qubit™ dsDNA HS Assay Kit and Invitrogen Qubit 2.0 Fluorometer. Then, cfDNA sequencing will be done on an Illumina HiSeq 3000. **RNA Sequencing.** Total RNA will be isolated from PBMC(25)(90). Purified RNA quality will be verified on an Agilent 2100 Bioanalyzer. RNA concentrations will be determined using a NanoDrop ND-1000 spectrophotometer. The mRNA library will be prepared with Illumina TruSeq RNA kit. The cDNA libraries will be quantitated using Qubit. Total mRNA will be amplified and sequenced on the whole-genome Illumina HiSeq 3000. **Flow Cytometry.** Immunophenotyping of PBMCs will be performed with 12-color monoclonal antibody panels to identify the subpopulations listed in **Table 2**. Cell fluorescence will be acquired on an LSR Fortessa™ cell analyzer, using standard acquisition templates. **Cytokine Quantification.** We will quantify plasma cytokine levels using a 38 multiplex Luminex array. Fluorescence intensity is acquired using a Luminex 200 instrument and xPONENT software.

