## SUMMARY

We propose to develop a tool that predicts adverse short- and long-term (within one year) outcomes for hospitalized COVID-19 patients. We hypothesize that new onset or worsening frailty, organ dysfunction and death from COVID-19 within one year after COVID-19 diagnosis can be accurately predicted by our algorithm that incorporates baseline genomic, transcriptomic, proteomic and clinical data. We will test our hypothesis in a mixed US COVID-19 population. We anticipate that a prediction test that performs well in the demographically and geographically diverse patient population that we will recruit will also demonstrate powerful prediction precision in the general population. Event prediction will assist clinicians in making tailored treatment plans. Future implementation of our tool into clinical settings may decrease morbidity and mortality, enhance patient quality of life and improve healthcare cost-effectiveness.

COVID-19 Functional Recovery Scale		
Least Severe	10	Not hospitalized, no limitations of activities
	9	Not hospitalized, limitation of activities and/or home oxygen requirement
	8	Hospitalized, not requiring supplemental oxygen and no longer requiring ongoing medical care (e.g. hospitalization for infection-control purposes)
	7	Hospitalized, not requiring supplemental oxygen but requiring ongoing medical care (COVID-19-related or other medical conditions)
	6	Hospitalized, requiring any supplemental oxygen
	5	Hospitalized, requiring noninvasive ventilation/high-flow oxygen devices
	4	Patients with single organ dysfunction defined by abnormalities in routinely collected laboratory parameters
	3	Patients with multi organ dysfunction
	2	Hospitalized, receiving invasive mechanical ventilation or extracorporeal membrane oxygenation (ECMO)
Most Severe	1	Death

**Figure 7** Tentative Ordinal COVID-19 Functional Recovery Scale.

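### After discharge, laboratory-detected organ dysfunction is recorded only in patients tested in routine care, so the organ part of the one-year endpoint is partly tied to care use

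*Protocol*

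**What the plan says.** All references are to the Protocol.

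- **Endpoint (RESEARCH PLAN, Endpoint Definition).** "Clinical composite endpoints will include new onset or worsening frailty, single organ dysfunction, multi-organ dysfunction, and death within one year (primary endpoint". The same composite at discharge is the secondary endpoint. No instrument or threshold is named here.
- **Timing (Data Collection, Clinical Data).** After listing laboratory values, organ function parameters and the SOFA, MELD-XI and Seattle scores, the paragraph states: "All clinical data will be collected at baseline, at discharge and at one year after COVID-19 enrollment".
- **Route.** The method needs "only one research blood draw at enrollment", and otherwise "abstraction of clinical parameters from the electronic medical record, and a brief interview at enrollment, at discharge, and at one year". The caption of Table 1 reads "Routine laboratory values to be abstracted from electronic medical record".
- **One-year contact.** "All patients will be interviewed in person (if not available, then by televisit) at discharge and one year after enrollment".
- **Back-up for lost patients.** The National Death Index "will be searched for subjects who are uncontactable".
- **Only working description of organ dysfunction (SUMMARY, Figure 7, a scale labelled tentative).** "Patients with single organ dysfunction defined by abnormalities in routinely collected laboratory parameters". Pitfall #4 lets this scale be assessed remotely or in person.

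**The concern.** The plan says that laboratory values and organ scores will exist at one year, but it provides no means of obtaining them. The only research draw is at enrollment. The one-year contact is a short interview. Everything else comes from whatever routine care has left in the chart. An inpatient will usually have these tests; a recovered outpatient may have none.

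At stake is the outcome label used in both aims. If post-discharge organ dysfunction is found mainly in patients who are tested often, part of the label measures testing. Testing plausibly follows comorbidity and care setting. Comorbidity scores are collected as clinical data, and Aim 2.1 adds a VA/civilian term to the models. An algorithm could therefore gain apparent accuracy by predicting who gets tested. The 200 validation patients of Aim 2.2 are labelled in the same way, so validation would not reveal it.

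**Working it through.** **1. The plan's own counts.** Sample Size Requirements assumes at least 20% endpoint-positive: 0.20 × 300 = 60 for training and 0.20 × 200 = 40 for validation. Both match the stated figures. The point concerns how positives are found, and contests neither count.

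**2. How each component can be found after discharge.**
- Death: interview, chart and National Death Index. Does not depend on care use.
- Frailty: a scale that can be scored at interview. Largely independent of care use.
- Organ dysfunction during the index stay: inpatient tests in the chart. Largely independent.
- Later organ dysfunction that led to a diagnosis or readmission: chart, and interview if asked. Partly dependent.
- Later organ dysfunction visible only in laboratory values: chart only. Fully dependent on a routine test having been ordered.

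Making the visit in person does not change the last line, because no blood draw is attached to it. The scores have the same difficulty. Preliminary Data, Study 1, calculated SOFA and MELD-XI in a study that collected bilirubin, creatinine, oxygen measures, blood pressure and the coma scale. A televisit does not supply such inputs.

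**3. Illustration of size.** The documents give no testing rates, so these inputs are assumptions:
- true composite rate 20% (the protocol's planning figure, for the whole composite);
- s = share of true positives detectable only by a post-discharge laboratory test, 25% to 75%;
- c = chance that a relevant test is in the chart, 40% to 80%;
- an untested patient is counted as negative (the protocol does not say this), and there are no false positives.

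Recorded rate = 0.20 × [1 − s(1 − c)].
- Mildest case, s = 0.25, c = 0.80: 0.20 × (1 − 0.05) = 19%, that is 38 of 200 and 57 of 300.
- Most severe case, s = 0.75, c = 0.40: 0.20 × (1 − 0.45) = 11%, that is 22 of 200 and 33 of 300.

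True positives among recorded negatives = 0.20 × s(1 − c) / (1 − recorded rate): 0.01/0.81 = 1.2% in the mildest case and 0.09/0.89 = 10.1% in the most severe.

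**4. Two groups with the same true rate of 20% but unequal testing.**
- s = 0.25, tested 90% vs 60%: 19.5% vs 18.0%, odds ratio (0.195/0.805)/(0.180/0.820) = 1.10.
- s = 0.50, tested 90% vs 40%: 19.0% vs 14.0%, odds ratio (0.190/0.810)/(0.140/0.860) = 1.44.
- s = 0.75, tested 90% vs 40%: 18.5% vs 11.0%, odds ratio (0.185/0.815)/(0.110/0.890) = 1.84.

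The true odds ratio is 1.0 in each case.

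**The case against.** The best reply has several parts.

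- **No instrument is named.** A reader might infer that SOFA, MELD-XI, the Seattle model and Table 1 are the stated definition of one-year organ dysfunction. They are listed only as data to be collected or calculated. The laboratory-based wording belongs to a tentative scale offered as an exploratory alternative. Thresholds, windows and missing-data rules may be in an analysis plan that is not shown. This stands, with one limit: an analysis plan cannot supply tests that were never done.
- **The endpoint is within one year, not at one year.** Dysfunction in the index stay or a readmission can count, which shrinks the affected share. This stands. What remains is dysfunction after discharge that never reaches a test. A cumulative reading also gives frequent attenders more chances to record an abnormal value.
- **Untested patients need not be called negative or dropped.** A reader might infer that these are the only two outcomes. The protocol says neither, and imputation or classification from interview and diagnoses is open.
- **Remote contact is only the fallback, and the promise covers all clinical data.** Both are true. But the promise is met by chart abstraction, and no follow-up test is scheduled.
- **A larger effect can be calculated.** Put the whole 20% on organ dysfunction, with tests in 80% of those affected and 40% of the rest. The recorded rate is then 0.20 × 0.80 = 16% with untested counted as negative, or 0.16/(0.16 + 0.80 × 0.40) = 33% with untested dropped. Testing 80% of affected Veterans and 50% of affected civilians gives 16% vs 10%, odds ratio 1.71. The arithmetic is right, but the 20% is for the whole composite, and nothing in the protocol says that Veterans are tested more.
- **The model comparison uses the same labels on both sides, and the setting term could absorb a setting-level difference.** This is partly true. It limits the harm to the clinical-versus-omics contrast, but does not make the label correct.

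**Conclusion.** The concern holds for one part of the composite: organ dysfunction arising after discharge and detectable only by laboratory test. For that part, the promise of complete one-year clinical data is not supported by the data collection the protocol describes, and the label depends partly on care use. A reader might conclude that the whole one-year label measures health-care use. The documents do not support that, since death, interview-scored frailty and in-hospital dysfunction are largely unaffected.

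The size cannot be computed from the documents. The recorded 11-19% and the odds ratios of 1.1-1.8 rest on assumed values of s and c and on counting untested patients as negative; the low end is small. That testing follows comorbidity and setting is plausible but not documented. This is worth correcting before one-year outcomes are collected, because items not asked in time may not be recoverable. It does not invalidate the design.

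**What to change.** Keep the composite endpoint and make four changes.

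1. Add to the one-year interview and the REDCap form a fixed set of organ-outcome items asked of every patient, in person or remote. Examples are new dialysis, home oxygen, a new organ-failure diagnosis and readmission, including care outside the site's own records.
2. For the one-year laboratory criterion, use only values from a fixed window around one year. Treat a patient without values as missing on that criterion, never as negative.
3. Report the share tested by endpoint status and by Veteran/civilian setting. Repeat the main AUC comparison with the organ component defined only by the items obtainable in every patient.
4. Do not rely on SOFA for one-year status where its inputs are not obtained.

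Cost: a few more interview items, some extra analysis, and more values recorded as missing. No added visit or blood draw is needed. The remedy is partial, because items based on diagnoses or readmissions still depend to some degree on care use. Asking everyone the same questions reduces the differential error without removing it.

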
**Sample Size Requirements and Power Calculations.** Current available literature suggests that at least 20% of the symptomatic COVID-19 infected population may develop frailty, organ dysfunction or death within one year(46, 47, 52, 56, 57, 61, 62, 113-116). Based on these assumptions, we will perform power calculations on the following numbers (250 civilians, 250 Veterans) (**Figure 2**): Aim 1.1 single-omic identification (n=100, 80 endpoint negative/20 endpoint positive) and confirmation (n=200, 160 endpoint negative/40 endpoint positive) of candidate genomic, transcriptomic, proteomic and clinical parameters that correlate with outcomes; Aim 1.2 multi-omics correlation analysis (n=300 from Aim 1.1, 240 endpoint negative/60 endpoint positive); Aim 1.3 WGCNA and pathway analysis (n=300 from Aim 1.1); Aim 2.1 training/testing of the predictive algorithm (n=300 from Aim 1.1); Aim 2.2 independent validation of predictive algorithm (independent n=200). Samples will be processed in 5 batches, approximately 120 samples per year within 5 years. Statistical analysis will begin after one-year outcomes of the first 100 patients have been collected. Patients will be stratified by outcomes, Veteran/civilian status, age, gender, ethnicity, comorbidities, frailty and other parameters that appear to be significant such as alcoholism.

**Timeline.** The timeline of the entire project is summarized in **Table 3**. We anticipate that: 1) recruitment of 600 COVID-19 patients will be begin 3 months after funding start, be completed within 42 months, 2) the 12-month follow-up period will be completed by month 57, and 3) the analysis will be completed by month 60.

Immune Cell Subsets	
Cell Population	Phenotype
T cells	CD3+CD4+ or CD3+CD8+
Naive	CCR7+CD45RA+
Effector Memory	CCR7-CD45RA-
Central Memory	CCR7+CD45RA-
TEMRA	CCR7-CD45RA+
Activated Effector	CD25++CD127hi
Regulatory	CD4+CD25++CD127lo
Antigen-experienced	KLRG1+
Limited capacity memory	CD38+
Chronically activated	CD57+
Activated suppressive	PD1+
Natural Killer Cells	CD3-CD56+
Cytotoxic	CD56dimCD16+
Cytokine producing	CD56brightCD16+
B Cells	CD19+
Transitional	CD38++CD24+
Mature Naive	CD27-IgD+
Memory	CD27+
Non-Switched memory	CD27+IgD-
Switched Memory	CD27-IgD+
Plasmablasts	CD27+CD38++
Regulatory	CD5+CD24+

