of the enrollment period. Thus, we expect to be able to complete the study as designed even if there is rapid implementation of an effective vaccine strategy that affects our ability to recruit subjects in the latter years of the project.

**Pitfall #3:** Our predictive algorithm does not perform well on certain subgroups. **Alternative:** We think this is unlikely because the biological responses (or lack thereof) that lead to poor outcomes are likely to be similar among people with differences in demographic and underlying diseases (182, 183). However, in the validation process, we will look at important subgroups to see if there are issues with performance. While we have guarded against a sub-group imbalance by proposing a dual strategy, combining a civilian population in one of the country's largest metropolitan areas and a representative National Veteran's population, it is possible that our algorithm may not be as accurate in predicting outcome in subgroups (e.g., women versus men). If this is the case, we will train the algorithm on the specific subgroup only and determine whether we identify different parameters. Using this approach, we may also uncover clues pointing to underlying pathogenic mechanisms in SARS-CoV-2 infection.

**Pitfall #4:** Currently, there is not enough data available to develop a clinical phenotype scale for COVID-19. **Alternative:** We will have a comprehensive outcome list and will be able to explore a more detailed way of characterizing COVID-19 outcomes by the end of our study. In order to better define clinical phenotypes, we will correlate molecular and clinical data from our 500 patients to a tentative 10-point COVID-19 Functional Recovery Scale, modified from the WHO 8-point ordinal scale (**Figure 7**)(44, 174). Since the COVID-19 landscape is continually changing, we will modify this scale as necessary. The COVID-19 Functional Recovery Scale scores will be assessed by tele-medicine or in-person visits at baseline, discharge (secondary endpoint) and one-year (primary endpoint). An ordinal scale of continuous phenotypes may provide better power for outcome prediction than a scale that only detects presence or absence of adverse outcome.

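### One-year outcomes rest on 500 completers, and the only source named for uncontactable patients is a death search, so the analysed events can tilt towards death

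*Protocol*

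**What the plan says.** In the Research Plan, the Patient Population paragraph sets the target: "We plan to complete 1-year follow-up in 500 patients". Loss is met by over-recruiting: "To account for a dropout rate of ~17%, we will recruit a total of 600 patients". The Endpoint Definition paragraph makes the primary endpoint a composite that includes "new onset or worsening frailty, single organ dysfunction, multi-organ dysfunction, and death within one year (primary endpoint"), with status at discharge as the secondary endpoint.

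Under Data Collection, clinical data come from the medical record and from interviews (in person or by televisit) and are due at baseline, discharge and one year. For patients who cannot be reached, the National Death Index "will be searched for subjects who are uncontactable". No other source is named for these patients in particular, and nothing says how one who is not found dead is classified.

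The Sample Size paragraph allots 100 + 200 patients to development and 200 to validation. Aim 2.2 repeats the 200, and Pitfall #4 again states that "we will correlate molecular and clinical data from our 500 patients". The laboratory plan is wider: "Samples will be processed in 5 batches, approximately 120 samples per year within 5 years".

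**The concern.** The death search can settle only one component of the composite, and in only one direction. It can make a lost patient endpoint positive through death. It cannot show that a lost patient became frail, developed organ dysfunction or stayed well. Where about one patient in six is expected to be lost, that asymmetry makes inclusion or classification depend on the outcome being predicted.

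The study's stated interest is in frailty and organ dysfunction as well as death. The Specific Aims foresee use in discussions about futility and in the allocation of scarce resources, and Aim 2.2 plans a free public web tool. Those uses rest on absolute risk, so the event rate, calibration and predictive values matter as well as discrimination. The 200 validation patients are ascertained in the same way as the 300 development patients, so the validation would not reveal a shift in event mix or base rate.

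**Working it through.** **1. The plan's own figure.** Recruitment = completers / (1 - loss).
- 500 / (1 - 0.17) = 602.4, or 603 rounded up; 500 / (1 - 1/6) = 600. The stated 600 is reproduced.
- Expected without one-year follow-up: 600 - 500 = 100, and 100 / 600 = 16.7%.
- The allotment 100 + 200 + 200 = 500, so no aim is sized on the other 100. The laboratory plan of 5 × 120 = 600 covers everyone enrolled.

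**2. What is known about a lost patient.**

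| True one-year status | Death search | One-year record abstraction |
|---|---|---|
| Died | Shows it | May show it |
| Organ dysfunction, alive | Cannot show it | May show it, if later records exist |
| Frailty, alive | Cannot show it | Not a stated source of the frailty score |
| Event-free | Cannot confirm it | Cannot fully confirm it |

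**3. Size under stated assumptions.** The protocol gives a composite rate: "at least 20% of the symptomatic COVID-19 infected population may develop frailty, organ dysfunction or death within one year". It does not give the split between death and non-fatal events, or loss by outcome. Assume 8% deaths and 12% non-fatal events: of 600, 48 die, 72 have a non-fatal event and 480 are event-free. Assume that all deaths are known and that the living lost are not classified from records. With loss a among non-fatal events and b among the event-free:
- events seen E = 48 + 72(1 - a)
- completers analysed N = E + 480(1 - b)
- rate if the living lost are dropped = E / N; if they are coded negative = E / 600
- deaths' share of events = 48 / E (true value 48 / 120 = 40%)

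| Loss a / b | E | N | Rate, dropped | Rate, coded negative | Deaths' share |
|---|---|---|---|---|---|
| 17% / 17% | 107.8 | 506 | 21.3% | 18.0% | 45% |
| 35% / 15% | 94.8 | 503 | 18.9% | 15.8% | 51% |
| 50% / 12% | 84.0 | 506 | 16.6% | 14.0% | 57% |

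The true rate is 20% throughout. In the second row 72 × 0.35 = 25 non-fatal events go unseen, and in the third 72 × 0.50 = 36. Under dropping, the rate can err either way. Under coding as negative, it errs downwards in all three rows. The tilt towards death is the same under both.

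**4. AUC.** Loss that depends only on the binary endpoint does not bias AUC. It can move through the event mix, or if loss also depends on predictors. Assume AUC 0.85 for death and 0.70 for non-fatal events, and take the composite as the event-weighted average (completers only): 0.40 × 0.85 + 0.60 × 0.70 = 0.760 with full follow-up, against 0.767, 0.776 and 0.786 in the three rows. The shift is 0.007 to 0.026.

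**5. Other assumptions.** Fix exactly 100 living losses, let deaths be 25%, 50% or 75% of the 120 events, and let patients with non-fatal events be lost 1 to 3 times as often as event-free patients. The observed rate among completers is then 16.8% to 22.8%. With AUCs of 0.85 and 0.75, the composite AUC moves by 0.004 to 0.015.

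**6. Bounds with no assumption about the lost.** With 100 events in 500 completers and 100 of unknown status, the one-year rate lies between 100 / 600 = 16.7% and 200 / 600 = 33.3%.

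**The case against.** A reader might infer that the protocol drops every living lost patient, or discards a patient who was endpoint positive at discharge and then lost. No sentence says either. Exclusion is the natural reading of a dropout allowance, but coding such patients negative or classifying them from records is equally compatible with the text. The protocol also does not say that patients found dead are added to the 500. On the wording "death within one year (primary endpoint) and at time of discharge (secondary endpoint"), a component met by discharge already falls within the year and would count.

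The medical record is a real second source. Abstraction at one year is planned for all patients, the laboratory table covers renal, hepatic, cardiac and coagulation values, and the tentative recovery scale defines single organ dysfunction by routine laboratory abnormalities. The gap is therefore widest for frailty and for confirming event-free status. The televisit option also reduces loss.

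The 500 can be read as a planning number, analysis populations and weighting are often left to a statistical analysis plan that is not shown here, and the death search prevents a worse error, missed deaths. The loss patterns and component AUCs above are assumed. Even so, the AUC shift is small beside the stated ±0.066 precision for the validation AUC. The main comparison is a difference of 0.12 between models in the same patients, and nothing here shows bias in it.

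All of this stands. It does not remove the asymmetry: the text gives uncontactable patients a dedicated route to one outcome only, and an analysis plan can weight the patients observed but cannot supply outcomes that were never collected.

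**Conclusion.** The point holds in a limited form. A completer target combined with a death-only search leaves living lost patients without a stated classification, and under either plausible handling the analysed events lean towards death. Under the assumptions in section 3, deaths' share of events rises by about 5 to 17 percentage points. The observed rate departs from 20% by between -3.4 and +1.3 points if these patients are dropped, and by -2.0 to -6.0 points if they are coded negative. Record abstraction would shrink these figures to an extent that the protocol does not allow one to estimate. What can be biased is the event rate, calibration and predictive values. The AUC effect is probably small, about 0.01-0.03. This is a worthwhile and cheap improvement, and the study does not stand or fall by it.

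**What to change.** 1. State under Endpoint Definition that a patient who meets any component at discharge, or in a later record within 12 months, is endpoint positive even without one-year contact. This spells out what the within-one-year wording already implies.
2. State under Data Collection that, for uncontactable patients, the planned one-year record abstraction is completed as well as the death search. Keep the death search.
3. Take all 600 enrolled and assayed patients as the base population, and do not code unknown status as negative. Report event rate, calibration and AUC with inverse-probability-of-follow-up weights, built from baseline and discharge data, alongside the completer analysis, and split the results by fatal and non-fatal events.

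The cost is a few sentences of protocol text, some extra abstraction and analysis, and slightly wider intervals from weighting. No further patients or samples are needed, because the processing plan already covers about 600 samples.

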**Aim 1.2: Multi-omics correlation analysis. Objective.** Genomics, transcriptomics and proteomics often have complementary roles to jointly perform a certain biological function and create a specific observable phenotype. Our objective in Aim 1.2 is to establish a correlation pattern between the multi-omics data and the outcome data in symptomatic COVID-19 patients. **Bioinformatics.** Multi-omics analyses will be performed on the first 300 samples to correlate outcome with cfDNA patterns, PBMC coding and non-coding mRNA expression, PBMC subpopulations and cytokine profiles (**Figure 2**). We will construct mixed effects regression models for each candidate feature. For continuous markers (cytokines) we will construct linear models. All logistic regression models will be stratified by primary composite outcome (single organ dysfunction, multiorgan dysfunction, and death). For count markers (sequencing), we will run negative binomial models. We will use the Benjamini-Hochberg procedure to control the FDR at alpha 0.05. If significant interaction effects are found after FDR adjustment, post hoc comparisons will be estimated using model contrasts and summarized with 95% confidence intervals estimated from the model. **Interpretation of Results.** Multi-omics correlations will add essential information in addition to the single omics analysis. We expect that the candidate genomic, transcriptomic, proteomic and clinical predictors will have distinct correlations within the two endpoint groups. This information can help characterize the biology of the immune response to COVID-19 and identify the most promising members for the prediction algorithm.

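### Table 2 gives switched memory B cells the same phenotype as mature naive B cells, outside the table's own definition of memory

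*Protocol*

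**What the plan says.** The Flow Cytometry paragraph of the Protocol's Research Plan (under Data Collection) states: "Immunophenotyping of PBMCs will be performed with 12-color monoclonal antibody panels to identify the subpopulations listed in" Table 2. The B-cell block of that table has the parent row CD19+ and seven subset rows. Four of the seven bear on this point:

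- Mature Naive: "Mature Naive CD27-IgD", with a plus sign after IgD, so CD27-IgD+.
- Memory: CD27+.
- Non-Switched memory: "Non-Switched memory CD27+IgD", with a minus sign after IgD, so CD27+IgD-. The run "Switched memory CD27+IgD" belongs to this row and not to the next one.
- Switched Memory: CD27-IgD+.

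The caption refers the reader to the text for details, but the text gives no other definition of any B-cell subset. Aim 1.2 (Bioinformatics) then uses the first 300 samples to "correlate outcome with cfDNA patterns, PBMC coding and non-coding mRNA expression, PBMC subpopulations and cytokine profiles". It fits a regression model for each candidate feature and controls the false discovery rate at 0.05 by Benjamini-Hochberg. Aim 2.1 builds the prediction models from the markers that pass the screening, with selection by LASSO.

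**The concern.** Two rows with different names and opposite biological meaning carry one phenotype. One of them is called memory but is CD27-negative, in a table where memory means CD27-positive. Both rows cannot be right.

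The subsets are candidate markers, so the definition matters. Applied literally, the Switched Memory variable would be a copy of the Mature Naive variable. An association of naive B cells with outcome would also appear as an association of switched memory cells. The Protocol expects leukocyte subpopulations to differ between endpoint groups (Aim 1.1, Interpretation of Results) and plans to release the raw data and the algorithm publicly (Aim 2.2), so a wrong label could reach other users.

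**Working it through.** No sample size, power or error rate is at issue, and the Protocol gives no figure to reproduce. The check compares the phenotypes in Table 2.

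**Step 1. Assign the four CD27/IgD combinations to rows.**

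| CD27 | IgD | Rows of Table 2 defined by that pair |
|---|---|---|
| + | + | none |
| + | - | Non-Switched memory |
| - | + | Mature Naive and Switched Memory |
| - | - | none |

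One combination is used twice. For comparison, the T-cell block of the same table splits on CCR7 and CD45RA and uses each of its four combinations once (Naive, Effector Memory, Central Memory, TEMRA). The rows and columns of the table read cleanly, so nothing suggests a text-extraction fault.

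**Step 2. Test the Switched Memory row against the parent Memory row.** Memory is CD27+ and Switched Memory is CD27-. The two sets have no cell in common, so by the table's own rule Switched Memory is not a memory subset.

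**Step 3. Look at the other memory row.** If Memory is CD27+ and is divided into switched and non-switched cells by IgD, one part must be CD27+IgD+ and the other CD27+IgD-. The table gives CD27+IgD- to the non-switched part. By common immunological naming, the IgD-negative part is the switched one. The Protocol does not state this, so this step is less secure than steps 1 and 2.

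**Step 4. Ask what is lost.** The cells in Memory (CD27+) that are not CD27+IgD- are the CD27+IgD+ cells. Their count therefore follows by subtraction from two rows that are defined. The population lacks a name and a row, but it can be recovered.

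**Step 5. Trace the duplicate through the analysis.**

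- Screening (Aim 1.2): two identical variables give two identical p-values. With m features and k rejections, the Benjamini-Hochberg cut-off is 0.05 × k/m. Adding a copy changes it to 0.05 × (k + 1)/(m + 1) if the feature is rejected, or 0.05 × k/(m + 1) if it is not. For large m either change is slight, but a single finding is counted as two.
- LASSO (Aim 2.1): for two identical columns with coefficients b1 and b2 of the same sign, the fit depends only on b1 + b2, and so does the penalty, because |b1| + |b2| = |b1 + b2|. The predictions, and hence the AUC, do not depend on how the weight is divided. Which of the two names is selected is arbitrary.

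The harm is therefore to naming and interpretation, with little effect on predictive performance.

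**The case against.** The strongest reply is that this is a slip in one or two table cells. The Table 2 caption presents the list as a demonstration of what the panels can do. Subsets are defined later in the analysis software, and nothing shows that these cells were copied into a template. An exactly duplicated column would probably be noticed at the data checks scheduled in Table 3. The Protocol also describes immunophenotyping as an addition that may improve on transcriptomic and clinical data.

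Much of this stands, and it limits the size of the point. It does not remove it, because the Flow Cytometry paragraph names Table 2 as the list to be identified and no other text corrects it.

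A reader might infer more than the Protocol supports:

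- *That one population goes unmeasured in all 600 patients.* CD27+IgD+ follows by subtraction (step 4), and both markers are acquired.
- *That switched memory cells are never measured.* If the usual naming applies, they are counted as CD27+IgD- under the opposite label.
- *That every B-cell result is compromised.* The two memory sub-rows are in question. Transitional, Mature Naive, Memory, Plasmablasts and Regulatory are not challenged.
- *That another laboratory could not reproduce the marker.* CD27-IgD+ is explicit and reproducible, although misnamed.

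**Conclusion.** The point holds in a limited form. The Protocol alone establishes that Switched Memory duplicates Mature Naive and conflicts with Memory being CD27+. That the Non-Switched row is also mislabelled is likely, but it rests on a naming convention from outside the document. At most two of the seven B-cell subset rows need correction.

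If the table is followed literally, one candidate feature enters the Aim 1 screening twice and the memory subsets carry wrong names. This assumes that the laboratory applies the phenotypes as printed, which the Protocol neither confirms nor rules out. Sample size, power and the primary endpoint are unaffected, since none of them depends on these definitions. The correction is small but should be made, because the subsets are screened against outcome and may be offered to the algorithm.

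**What to change.** Reconcile the two memory rows of Table 2 so that both lie within CD27+ and are separated by IgD. By convention this gives Non-Switched memory as CD27+IgD+ and Switched Memory as CD27+IgD-; the flow cytometry laboratory should confirm it. Keep Mature Naive as CD27-IgD+. Lock the definitions in the cytometry analysis template before the first batch is analysed, so that all five planned batches use one set, and re-analyse any files already acquired.

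The cost is two table cells and the matching template entries. CD27 and IgD already appear among the listed phenotypes, so no new reagent or patient sample is needed.
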